16.1.5.2 Estimation of Pharmacokinetic Parameters in Urine

Urine concentrations which are BLQ will be set to zero.

The following urine PK parameters will be calculated for metformin:

Symbol	Definition
A_{e0-36}	The cumulative amount excreted from time zero (= dosing time) to the end of the collection interval after dosing, calculated for metformin only.
CLR	Renal clearance. $CLR = A_{e0-36}/AUC_{0-36}$, calculated for metformin only.

16.1.6 Presentation of PK Concentration and PK Parameter Data

For participants determined to have transporter polymorphism status of “poor” for a specific transporter (e.g., homozygous with 2 alleles defective for a transporter), these individuals will be excluded from the primary statistical analyses for the relevant substrate; however, data for all participants will additionally be summarized and analyzed using sensitivity analyses.

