To characterize the effect of evobrutinib on digoxin, metformin, and rosuvastatin (Part 1), and sumatriptan (Part 2) secondary PK parameters in healthy participants	
Plasma PK parameters (Part 1 and Part 2): t_{max}, $t_{1/2}$, and $AUC_{0-tlast}$, CL/F, and Vz/FUrine PK parameters (Part 1, metformin only): Ae_{0-36} and CL_R

CCI

CL/F=apparent total body clearance, CL_R=renal clearance, ECG= electrocardiogram, PK=pharmacokinetics, TEAE=treatment-emergent adverse event, Vz/F= apparent volume of distribution.

6 Overview of Planned Analyses

The final, planned analyses identified in the CSP and in this IAP will be performed after the last participant has completed the last visit and after all data queries resolved as well as the database locked.

A data review meeting will be held prior to database lock for the final analysis. In addition, no database can be locked until this IAP has been approved.

7 Changes to the Planned Analyses in the Clinical Study Protocol

There are no changes to the planned analyses in the clinical study protocol.

8 Analysis Sets and Subgroups

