8.1 Definition of Analysis Sets

Analysis Set	Description
Screening	All participants, who provided informed consent, regardless of the participant's enrollment and study intervention status in the study.
Safety (SAF)	All participants, who were administered any dose of any study intervention. Analyses will consider participants as treated.
Pharmacokinetic (PK)	
The PK Analysis Set is a subset of the SAF, and the PK population will include all participants:
 
• Who have completed the study without any relevant protocol deviations and factors likely to affect the comparability of PK results.• With adequate study intervention compliance. 
With evaluable PK data, i.e., no missing values for primary endpoints at each PK profile/assessment day (Day 1, Day 10 for Part 1; Day 1 and Day 8 for Part 2).
 
If participants received prohibited concomitant therapy or medicines, as specified in Section 6.8.3 of the protocol, they will be excluded from the PK population.
 
All PK analyses will be based on this analysis set.

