16.1 Pharmacokinetics

PK evaluation will be performed by Nuvisan GmbH.

All statistical analyses and descriptive summaries of PK data will be performed on the PK Analysis Set.

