16.1.3 Statistical Analysis of PK Parameter Data

Part 1

- **Analysis of Primary Endpoints**

A general linear model with a fixed effect for TREATMENT and a random effect for SUBJECT will be applied to log-transformed PK parameters C_{max} and $AUC_{0-\infty}$ based on the PK analysis set to assess the effect of multiple doses of evobrutinib on the PK of the transporter substrates digoxin, metformin, and rosuvastatin. Treatment differences on the log scale of transporter substrates with evobrutinib vs substrates alone (Day 10 versus Day 1) will be estimated for C_{max} and $AUC_{0-\infty}$ together with their 90% CIs.

Point estimates and CIs will be back transformed to the original scale.

- **Analysis of Secondary Endpoints**

[figure not shown]
The same analysis model as described for the primary endpoints will be provided for the secondary endpoint $AUC_{0-t_{last}}$ of transporter substrates.

The same analysis model as described for the primary endpoints will be provided for the secondary endpoint CL_R of metformin only.

Sensitivity Analyses

The same analyses on the primary and secondary endpoints will be repeated including participants
CCI

Part 2

- **Analysis of Primary Endpoints**

A general linear model with a fixed effect for TREATMENT and a random effect for SUBJECT will be applied to log-transformed PK parameters C_{max} and $AUC_{0-\infty}$ based on the PK analysis set to assess the effect of multiple doses of evobrutinib on the PK of the transporter substrate sumatriptan. Treatment differences on the log scale of sumatriptan with evobrutinib vs sumatriptan alone (Day 8 versus Day 1) will be estimated for C_{max} and $AUC_{0-\infty}$ together with their 90% CIs.

Point estimates and CIs will be back transformed to the original scale.

- **Analysis of Secondary Endpoints**

The same analysis model as described for the primary endpoints will be provided for the secondary endpoint $AUC_{0-t_{last}}$ of sumatriptan.

Sensitivity Analyses

The same analyses on the primary and secondary endpoints will be repeated including participants
CCI

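### Does the SAP name two different primary populations when it leaves out participants with a poor transporter genotype?

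*SAP*

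**What the plan says.** Protocol 9.3 and SAP 8.1 define the PK Analysis Set participant by participant: study completed without relevant deviations, adequate compliance, primary endpoints available on both profile days, no prohibited medication. SAP 8.1 adds "All PK analyses will be based on this analysis set", and SAP 16.1 repeats it: "All statistical analyses and descriptive summaries of PK data will be performed on the PK Analysis Set". The Part 1 primary paragraph of SAP 16.1.3 runs the model "based on the PK analysis set to assess the effect of multiple doses of evobrutinib on the PK of the transporter substrates". The Part 2 paragraph does the same for sumatriptan, and Protocol 9.4.3 matches both.

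SAP 16.1.6, a section on presentation, then says of participants with poor status for a transporter that "these individuals will be excluded from the primary statistical analyses for the relevant substrate". It continues that "data for all participants will additionally be summarized and analyzed using sensitivity analyses". Its only description of poor is an example: two defective alleles.

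SAP 16.1.3 also has, for each part, a sensitivity paragraph that repeats the primary and secondary analyses with some further participants included. The words naming that group are blacked out. SAP Section 7 states: "There are no changes to the planned analyses in the clinical study protocol".

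**The concern.** The set definition is fully visible and does not mention genotype. Read alone, SAP 8.1, 16.1 and the primary paragraphs of 16.1.3 put every member of the set into the primary model. Read alone, 16.1.6 takes some of them out. Two programmers working from different sections could produce different primary ratios for the same endpoint.

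Three things make this look worse. The rule stands under a heading where few would look for it. Section 7 declares no departure from a protocol whose visible analysis sections contain no such exclusion. And because poor is given only by example, the excluded list could in principle be settled after open-label PK results are known.

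At stake would be the point estimate and its 90% interval, which are the study's whole result. Exclusion also moves the question from healthy participants in general to healthy participants with a working transporter, and it reduces the roughly 16 evaluable participants per part.

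**Working it through.** **Do the sections conflict?**

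1. SAP 8.1 ties all PK analyses to the set. It does not say that every member enters every model. The SAP already separates the two elsewhere: 10.2.1 allows individual values to be flagged for exclusion, and 16.1.4 drops affected concentrations and parameters from further statistical evaluation. A substrate-level exclusion inside the set follows the same pattern.
2. Under that reading the set holds all genotypes, the primary analysis for a substrate uses the set without those poor for the relevant transporter, and the sensitivity analysis uses the whole set. SAP 8.1, 16.1, 16.1.3 and 16.1.6 can then all be followed.
3. The general criterion in 8.1, "Who have completed the study without any relevant protocol deviations and factors likely to affect the comparability of PK results", is not needed to justify the exclusion and would serve it badly. The set is defined per participant, so in Part 1 it would remove someone from digoxin, metformin and rosuvastatin together, whereas 16.1.6 removes them only for the substrate concerned.
4. A sensitivity analysis that adds participants, as in 16.1.3, implies that the primary analysis left some out. This agrees with 16.1.6.
5. Protocol 4.2 already warns that polymorphic transporters could affect interpretation and provides for samples, whose type is blacked out. Text is also blacked out between Protocol 8.4 and 8.6, at 9.2, within 9.4.2 and at Appendix 6. Whether the genotype rule stands there cannot be known, so Section 7 cannot be shown to be wrong.

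**How far apart could the two estimates be?**

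There is no plan figure to reproduce: the precision tables are blacked out, and neither the frequency of poor genotypes nor their response is given. The only inputs from the documents are about 16 evaluable per part (Protocol 1.1) and the 90% interval (Protocol 9.4.3). The rest is assumed.

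*Point estimate.* Assume a true ratio R in participants with a working transporter and 1 in the k poor ones. The model averages log ratios, so the all-participant ratio is R^((16−k)/16).

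| R (poor excluded) | k = 1 | k = 2 | k = 3 |
|---|---|---|---|
| 1.25 | 1.23 | 1.22 | 1.20 |
| 1.50 | 1.46 | 1.43 | 1.39 |
| 2.00 | 1.92 | 1.83 | 1.76 |

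For example, 1.50^(14/16) = exp(0.4055 × 0.875) = 1.43. If poor participants respond like the others, the two ratios agree in expectation.

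*Precision.* On the log scale the half-width is proportional to t(0.95, n−1)/√n.

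- n = 16: 1.753/4.000 = 0.438
- n = 15: 1.761/3.873 = 0.455, 4% wider
- n = 14: 1.771/3.742 = 0.473, 8% wider
- n = 13: 1.782/3.606 = 0.494, 13% wider

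With s = √ln(1+CV²), the limits are the ratio times exp(±t·s·√(2/n)). The table gives these multipliers for assumed intra-subject CVs.

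| CV | n = 16 | n = 14 |
|---|---|---|
| 20% | 0.884 to 1.131 | 0.876 to 1.142 |
| 30% | 0.834 to 1.200 | 0.822 to 1.217 |
| 40% | 0.788 to 1.270 | 0.773 to 1.294 |

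*Would anyone be excluded?* The chance of at least one poor participant among 16 is 1 − (1−p)^16. For assumed frequencies of 1%, 5%, 10% and 15% it is 15%, 56%, 82% and 93%.

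**The case for a change.** The strongest case for a change is that the primary paragraphs name the PK Analysis Set with no exception, while the rule deciding who enters the primary estimate appears only under presentation. That the sponsor's intent can be inferred makes the repair easy but does not write it down. Poor is also under-specified: Protocol Table 3 pairs metformin with two transporters, MATE1 and MATE2-K, and 16.1.6 does not say whether a defect in one is enough. No visible text withholds PK results until the list is fixed.

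The drafting criticism stands: a cross-reference in 8.1 or 16.1.3 and a list of genotypes would be better practice. It carries less weight than it seems to, for three reasons. Genotype is fixed before dosing and cannot be influenced by treatment. Each comparison is within participant, so leaving someone out removes both of their profiles and creates no imbalance. Exclusions are settled at a data review meeting before database lock (Protocol 9.3), and lock itself requires an approved analysis plan (SAP Section 6). Some freedom over the list may remain, but a choice that mattered would show as a gap between the two planned estimates.

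The alternative of making all genotypes primary is a trade-off. It matches the stated objective in healthy participants more literally. However, Protocol 2.1 aims to learn the effect on transporter activity, and people who lack the transporter may dilute that effect, as the first table shows.

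**Conclusion.** No change is needed. The specific rule in SAP 16.1.6 says which analysis is primary and which is sensitivity, the sensitivity paragraphs of 16.1.3 agree with it, and the set definition can accommodate it. The charge that Section 7 is false cannot be made from documents with relevant text blacked out.

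The gap between the two estimates runs from nothing, if nobody is poor, to 1.50 against 1.39 or 2.00 against 1.76 with three poor among 16, with log-scale intervals 4% to 13% wider for one to three exclusions. These figures rest on an assumed ratio of 1 in poor participants and on assumed counts. Both estimates are planned and Protocol 9.1 rules out hypothesis tests, so no test decision depends on which is called primary. A team following the plan would reach a sound conclusion. The missing cross-reference and the per-transporter meaning of poor, unless the latter is in the blacked-out text, are details that analysts would ordinarily settle by the data review meeting.

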16.1.6.1 Listings and Tables

The following PK tables will be produced (PK Analysis Set) by part:

- Descriptive statistics of concentrations by analyte, matrix, study intervention (day)
- Descriptive statistics of PK parameters by analyte, matrix, study intervention (day)

The following PK Listings will be produced (Safety Analysis Set) by part:

[figure not shown]
- Individual concentrations, nominal time by participant, analyte, matrix, day and study intervention (day) sorted in chronological order
- Individual PK parameters by participant, analyte, matrix, day and study intervention (day) sorted in chronological order
- PK Sampling date, actual time, nominal time, deviation from time, percentage time deviation by participant, analyte, matrix and study intervention (day) sorted in chronological order
- Start and end time and date of collection interval, urine volume, concentration, excreted amount by participant, analyte, matrix and study intervention (day) sorted in chronological order
- Phoenix WinNonlin NCA Core Output

16.1.6.2 Graphical Summaries and Individual plots (PK Analysis Set)

The following graphical summaries and individual plots will be provided for digoxin, metformin, and rosuvastatin in plasma of Part 1 and sumatriptan in plasma of Part 2:

- Overlaid individual plasma concentration versus time plots on linear and semi-log scale, using actual times; by analyte and study intervention (day)

- Overlaid individual plasma concentration versus time plots by participant and analyte on linear and semi-log scale using actual times. If any post-dose concentration is BLQ the line representing LLOQ will be added to the semi-log plots
- Arithmetic mean concentration time plots; linear (\pm SD for arithmetic mean) and semi-log; using scheduled (nominal) time points by day, analyte, matrix and group; if any post-dose concentration is BLQ the line representing LLOQ will be added to the semi-log plots
- Median concentration time plots; linear and semi-log; using scheduled (nominal) time points by day, analyte, matrix and group; if any post-dose concentration is BLQ the line representing LLOQ will be added to the semi-log plots
- Boxplots for primary PK parameters ($AUC_{0-\infty}$ and C_{max}) by study intervention (day) and analyte
- Spaghetti plot of primary PK parameters by study intervention (day) and analyte

17

References

Not applicable.

18 Appendices

Not applicable.
